9.2.4.2 Study Medication Discontinuation

Study medication should be permanently discontinued in the event of any of the following:

- Severe infection requiring parenteral antimicrobial therapy or hospitalization
- Symptomatic herpes zoster
- Malignancy – except for non-melanoma skin cancer (SCC or BCC) not in or near the treatment area
- Anaphylactic or severe allergic reaction
- WBC Count: < 1 x 10⁹/L or second occurrence of < 2 x 10⁹/L
- ANC:< 0.5 x 10⁹/L or second occurrence of < 1 x 10⁹/L
- Lymphocyte count:< 0.3 x 10⁹/L or second occurrence of < 0.5 x 10⁹/L
- Platelet count: < 50 x 10⁹/L or second event of < 75 x 10⁹/L - in each case, value should be confirmed by retesting before treatment discontinuation
- Hemoglobin: < 6.5 g/dL or second occurrence of < 8 g/dL - in each case, value should be confirmed by retesting before treatment discontinuation
- AST or ALT:
 - > 5 x ULN persisting for 2-weeks of study medication interruption or second event of > 5 x ULN
 - > 3 x ULN with total bilirubin >2 x ULN or symptoms of hepatocellular injury [fatigue, nausea, vomiting, right upper quadrant pain or tenderness, fever, rash and/ or eosinophilia (>5%)].

- Serum creatinine: $> 2 \times \text{ULN}$ persisting for >2 weeks of treatment discontinuation or second occurrence of $> 2 \times \text{ULN}$

The continued treatment of subjects who experience other serious or severe adverse events considered related to study treatment should be discussed with the Sponsor's medical monitor.

10. PREGNANCY

10.1. Definition of Women of Child Bearing Potential (WOCBP)

WOCBP includes any female who has experienced menarche and who has not undergone successful surgical sterilization (e.g., hysterectomy, bilateral tubal ligation, or bilateral oophorectomy) or is not postmenopausal. Postmenopausal is defined as ≥ 12 months with no menses without an alternative medical cause. WOCBP must have a negative serum pregnancy test at screening and a negative UPT at baseline prior to application of study medication.

10.2. Highly Effective Methods of Birth Control

The Investigator or subinvestigator will discuss the potential risk factors associated with pregnancy and the importance of maintaining a highly effective method of contraception throughout the study with all WOCBP (for example, those which result in a low failure rate - i.e., less than 1% per year-when used consistently and correctly). All WOCBP must use a highly effective method of birth control during the study and for 30 days after the final application of study medication in a manner such that risk of failure is minimized.

Highly effective methods include:

- Combined (estrogen and progestogen containing) hormonal contraception associated with inhibition of ovulation:
 - oral
 - intravaginal
 - transdermal
- Progestogen-only hormonal contraception associated with inhibition of ovulation:
 - oral
 - injectable
 - implantable
- intrauterine device (IUD)
- obstruction of fallopian tubes via medical device (Essure TM)
- intrauterine hormone-releasing system (IUS)
- vasectomized partner¹
- sexual abstinence²

¹Vasectomized partner is a highly effective birth control method provided that partner is the sole sexual partner of the WOCBP trial participant and that the vasectomized partner has received medical assessment of the surgical success.

² Sexual abstinence is considered a highly effective method only if defined as refraining from heterosexual intercourse during the entire period of risk associated with the study treatments. The reliability of sexual abstinence needs to be evaluated in relation to the duration of the clinical trial and the preferred and usual lifestyle of the subject.

WOCBP must be on a highly effective method of birth control for the following timeframes prior to study entry:

- Implants (on a stable dose for ≥ 30 days)
- Injectables (on a stable dose for ≥ 30 days)
- Patches (on a stable dose for ≥ 30 days)
- Combined oral contraceptives (on a stable dose for ≥ 30 days)
- Intrauterine devices (inserted for ≥ 30 days).

Prior to trial enrollment, WOCBP must be advised of the importance of avoiding pregnancy during trial participation and of the potential risk factors associated with pregnancy while in the study. The subject must sign an informed consent form documenting this discussion. During the trial, all WOCBP will be instructed to contact the investigator immediately if they suspect they might be pregnant (*e.g.*, missed or late menstrual period).

If a subject or investigator suspects that the subject may be pregnant prior to study medication administration, the study medication must be withheld until the results of a pregnancy test are available. If pregnancy is confirmed, the subject must not receive study medication and must be discharged from the study.

If, following study medication administration, it is determined that the subject may have been or was pregnant at the time of study medication exposure (including at least 2 days after study medication administration) the investigator must immediately notify the Aclaris Therapeutics, Inc. Medical Monitor and record the event on a pregnancy surveillance form. While not an AE or SAE, the investigator must report every pregnancy using a pregnancy surveillance form and follow the reporting procedures described for SAE reporting.

Protocol-required procedures for trial discontinuation and follow-up must be performed on the subject unless contraindicated by pregnancy (*e.g.*, x-ray studies). Other appropriate pregnancy follow-up procedures should be considered if indicated. In addition, the investigator must report to Aclaris Therapeutics, Inc.'s Medical Monitor on the pregnancy surveillance form, follow-up information regarding the course of the pregnancy, including perinatal and neonatal outcome. Infants should be followed for a minimum of six weeks.

11. STATISTICAL ANALYSES

11.1. Sample Size and Power Calculations

Thirty-three subjects will be enrolled. This is a pilot study and the first study with ATI-50002 Topical Solution for the treatment of facial vitiligo. A formal power calculation was not performed. The initial analyses will be performed after all subjects complete Visit 10 (Week 24).

11.2. Statistical Methods

Summary descriptive statistics (N, mean, median, SD) by visit will be provided for all safety and efficacy parameters. Primary and secondary efficacy parameters are described below:

Primary Efficacy Parameter

Mean change from baseline in facial depigmentation in the AOI will be quantified using Canfield-2-D photographic image analysis from baseline (Visit 2) compared to Week 48 (Visit 14).

Secondary Efficacy Parameters:

Mean change from baseline in facial depigmentation will be calculated as the mean change in Facial assessment of the Vitiligo Area Scoring Index (F-VASI) from Visit 2 compared to Week 24 (Visit 10) and if applicable, Week 48 (Visit 14). F-VASI is a modification of the validated quantitative assessment scale for vitiligo which evaluates the percentage of vitiligo involvement of the face only.

Mean change from baseline in facial depigmentation in the AOI based on Canfield 2-D Photographic analysis from Visit 2 compared to Weeks 4, 8, 12, 16, 20, 24, 32, 40, and post-treatment Week 52 (Visits 5-11, and 12, 13, and 15).

Mean change from baseline in the Facial assessment of the Vitiligo Area Scoring Index (F-VASI) from Visit 2 compared to Weeks 4, 8, 12, 16, 20, 24, 32, 40, 48 and post-treatment Week 52 (Visits 5-11, and Visits 12, 13, 14 and 15).

Mean change from baseline in the VitiQoL from Visit 2 compared to Week 12, 16, 20, 24, and 48 (Visits 7-10, 14).

Treatment success based on the subject's assessment of vitiligo on the Vitiligo Noticeability Scale (VNS) at Week 4, 8, 12, 16, 20, 24, 32, 40, and 48.

Mean change from baseline in total VASI from Visit 2 to Visits 7 and Visit 14 (Week 48) will be assessed for descriptive purposes only to track disease progression in untreated areas.

Safety analyses will include descriptive statistics calculated on the safety parameters using the safety population. The proportion of subjects with treatment-emergent adverse events will be tabulated and presented by Medical Dictionary for Regulatory Activities (MedDRA) System Organ Class. Vital signs and clinically relevant abnormal laboratory results will also be tabulated and presented. Change from baseline in the Local Tolerability Assessments (LTA) to end of treatment (Visit 10) will be summarized.

Data from all enrolled and treated subjects will be presented and summarized. Safety summaries by study will include listings of adverse events incidences within each MedDRA System Organ Class, and changes from pre-application values in vital signs. Adverse event summaries will be presented showing the proportion of subjects experiencing adverse events, both overall and by MedDRA System Organ Class.

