 2. Clinically significant heart rate \leq 45 or Heart Rate \geq 100 beats/minutes
 3. Rhythm disturbance other than sinus arrhythmia or ectopic supraventricular rhythm (ectopic atrial rhythm)
 4. Conduction disturbance including PR >240msec, pre-excitation (delta wave and PR <120msec), second degree or higher AV block
 5. Acute or chronic signs of ischemia.
 6. Left Bundle Branch Block
 7. Prior myocardial infarction
22. Positive for HIV, Hepatitis B or C. Subject with serologic evidence of Hepatitis B vaccination (HepB surface Ab without the presence of Hep B sAg) will be allowed to participate.

Duration of Treatment

The planned study durations are:

- Enrollment period: 12 weeks (84 days)
- Study participation duration (Visit 1 through Visit 11 is a maximum of 229 days).
- Duration of study participation from Visit 1 thought Visit 15 is a maximum of 372 days.

Criteria for Evaluation:*Efficacy:*

The percentage of facial depigmentation will be quantified in the Area of Interest (AOI) through analysis of digital images (Section 8.1.1 Canfield 2D Digital Facial Image Analysis).

The investigator will evaluate facial repigmentation using the Facial Assessment of the Vitiligo AreaScoring Index (F-VASI).

Subject will assess facial repigmentation using the Vitiligo Noticeability Scale (VNS). Treatment success will be defined as follows: VNS score of 1 or 2 = treatment not successful, VNS score of 3 = treatment partially successful, or VNS score of 4 or 5 = treatment successful.

Safety:

The investigator will assess clinical laboratory safety tests, vital signs, ECGs, concomitant therapies, urine pregnancy test results, and adverse events (AEs) throughout the study.

Other:

The investigator will assess the extent of vitiligo using the VASI (total body). VASI will be assessed for descriptive purposes only to track disease progression in untreated areas.

Subjects will assess their satisfaction with the results of the study using the Subject Vitiligo Satisfaction scale.

Subjects will assess the impact of vitiligo on their quality of life using the VitiQoL.

Study Medication Administration

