Mean change from baseline in total VASI from baseline (Visit 2) to Week 4, 8, 12, 16, 20 24 and 48 (Visits 5-15) will be assessed for descriptive purposes only to track disease progression in untreated areas.

Safety analyses will include descriptive statistics calculated on the safety parameters using the safety population. The proportion of subjects with treatment-emergent adverse events will be tabulated and presented by treatment and Medical Dictionary for Regulatory Activities (MedDRA) System Organ Class. Vital signs and clinically relevant abnormal laboratory results will also be tabulated and presented. Change from baseline (Visit 2) in the Local Tolerability Assessments (LTA) to end of treatment (Visit 10) will be summarized.

Data from all enrolled and treated subjects will be presented and summarized. Safety summaries will include listings by study medication of adverse events incidences within each MedDRA System Organ Class, and changes from pre-application values in vital signs. Adverse event summaries will be presented showing the proportion of subjects experiencing adverse events, both overall and by MedDRA System Organ Class.

TABLE OF CONTENTS

1. SYNOPSIS	6
2. INTRODUCTION.....	18
2.1. Summary.....	18
3. STUDY RATIONALE.....	20
3.1. Study Rationale.....	20
4. STUDY OBJECTIVES	20
4.1. Primary Objective	20
4.2. Secondary Objectives	20
5. SELECTION AND DISPOSITION OF STUDY POPULATION	20
5.1. Number of Subjects and Study Sites	20
5.2. Study Population Characteristics.....	20
5.3. Inclusion Criteria.....	21
5.4. Exclusion Criteria.....	21
5.5. Previous and Concomitant Medications and Therapies.....	23
5.6. Permitted Concomitant Medications, Therapies and Over the Counter Products (OTC)	23
5.6.1. Prohibited and/ or Restricted Medications	24
5.7. Subject Identifier (SI)	24
5.8. Replacement Subjects	25
5.9. Subject Withdrawal Criteria	25
5.10. Study Termination	25
6. INVESTIGATIONAL PLAN.....	26
6.1. Overall Study Design.....	26
6.2. STUDY PROCEDURES	26
6.3. Schedule of Assessments	27
6.4. Study Visits Description and Procedures	30
6.4.1. Visit 1/ Screening (Day -28 to 0)	30
6.4.2. Visit 2 (Day 1) / Baseline.....	30
6.4.3. Visit 3-9 (Weeks 1, 2, 4, 8, 12, 16 and 20) These visits must occur on the following weeks after Visit 2:	32
6.4.4. Visit 10 (Week 24).....	32
6.4.5. Visit 11 (Week 28).....	33
6.4.6. Visit 12 (Week 32).....	34

6.4.7. Visit 13 (Week 40).....	34
6.4.8. Visit 14 (Week 48).....	35
6.4.9. Visit 15 (Week 52).....	35

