8.1.4. Vitiligo Area Scoring Index (VASI)

The VASI will be assessed by the investigator or designee to track the total body vitiligo status throughout the study at screening (Visit 1), baseline (Visit 2), Week 12 (Visit 7), Week 24 (Visit 10), and Week 48 (Visit 14). The body is divided into the following 6 separate and mutually exclusive sites: head/neck, hands, upper extremities (excluding hands), trunk, lower extremities (excluding feet), and feet. The investigator or designee will assess each of the 6 body sites using a Wood's lamp to assist in the identification of the vitiliginous lesions.

The percentage of vitiligo involvement for each body region is calculated using the palmar method. The palmar method uses the palmar surface area of the investigator or designee's hand as an estimation guide and defines the surface of the evaluator's hand including fingers to be 1.0% of the total body surface area. Each of the 6 body sites is then clinically evaluated by visual assessment for the pattern of skin depigmentation using a visual scale. The publication by Hamzavi I, Jain H, McLean D, Shapiro J, Zeng H, and Lui H. 2004 will be provided to the investigators to depict the pattern of depigmentation as illustrated in descriptive patient photographs.

Total body VASI = Sum of all the values from the body sites (in Hand units) x (Residual depigmentation)

- **Hand unit** - One hand unit is approximately 1% BSA – used as a guide to estimate % of vitiligo involvement in each body area. (Body is divided into 6 areas)
- **Extent of residual depigmentation** is expressed by the following percentages:
 - 0
 - 10% - only specks of depigmentation are present
 - 25% - the pigmented area exceeds the depigmented area
 - 50% - the depigmented and pigmented areas are equal
 - 75% - the depigmented area exceeds the pigmented area
 - 90% - specks of pigment are present
 - 100% - no pigment is present

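### Total VASI is presented as tracking untreated skin, but its six-site sum includes the treated head/neck, and no summary without head/neck is planned

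*Combined protocol and SAP*

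**What the plan says.** The synopsis (Criteria for Evaluation, Other) states that "VASI will be assessed for descriptive purposes only to track disease progression in untreated areas". Section 11.2 repeats the purpose for the planned summary, the mean change in total VASI from Visit 2, which "will be assessed for descriptive purposes only to track disease progression in untreated areas".

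Section 8.1.4 describes the instrument differently. Its purpose there is "to track the total body vitiligo status throughout the study". The sites are "head/neck, hands, upper extremities (excluding hands), trunk, lower extremities (excluding feet), and feet", and the score is defined by "Total body VASI = Sum of all the values from the body sites", each in hand units multiplied by residual depigmentation. The sites are scored one at a time: "Each of the 6 body sites is then clinically evaluated by visual assessment for the pattern of skin depigmentation using a visual scale".

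Sections 6.1 and 7.3 direct treatment to vitiliginous areas of the face and neck with a margin around them. Section 7.3 also has new face or neck patches treated. Section 11.2 plans no breakdown of VASI by body site.

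**The concern.** The score contains the treated skin it is meant to leave out. Three consequences follow.

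- Improvement on the face or neck can cancel worsening elsewhere, so spread in untreated skin can go unseen.
- New patches on the face or neck raise the total and can be read as progression in untreated skin.
- Inclusion criterion 2 (Section 5.3) allows non-facial lesions but does not require them. For a subject with none outside head/neck, the baseline total is entirely head/neck.

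Total VASI is the only scheduled extent score that covers skin beyond the face and neck. Section 7.3 says that new vitiligo on the face or other body areas is not an adverse event, so the adverse event tables will not show spread either. The physical examination (Section 8.2.2) includes the skin but yields no extent score.

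**Working it through.** The plan gives no figure to reproduce: Section 11.1 reports no power calculation, and no baseline VASI or expected response appears anywhere. The check is a comparison of the texts followed by an illustration on assumed values.

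**Text.** The purpose (synopsis, 11.2) is untreated areas. The definition (8.1.4) is all six sites, including head/neck. The treated skin (6.1, 7.3) is face and neck. The planned output (11.2) is the total only. The purpose and the definition cannot both stand.

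**Can F-VASI separate the two?** Not fully. Appendix 6 confines F-VASI to the photographic mask and leaves out beard areas. The neck is treated but lies outside F-VASI. Appendix 6 also lets staff have subjects treat the forehead and chin areas behind the positioning device, the eyebrow area and the beard area. Total VASI minus F-VASI would still contain treated skin.

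**Arithmetic.** Let H be the mean head/neck score, O the mean sum of the other five sites, r the fractional fall in head/neck and g the fractional rise elsewhere. One unit is one hand unit (about 1% of body surface) at full depigmentation. Because the score is a sum,

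mean change in total = -H × r + O × g.

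The rise elsewhere that is fully hidden is H × r units, or H × r / O as a share of the other-site baseline. All inputs are assumptions, except that H = 0.25 corresponds to the 0.25% facial entry minimum at full depigmentation.

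| H | r | Hidden, units | O = 1 | O = 3 | O = 20 |
|---|---|---|---|---|---|
| 1 | 0.50 | 0.5 | 50% | 16.7% | 2.5% |
| 1 | 0.25 | 0.25 | 25% | 8.3% | 1.25% |
| 0.25 | 0.50 | 0.125 | 12.5% | 4.2% | 0.6% |

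Worked cases with H = 1 and g = 0.10:

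- O = 3, r = 0.50: other sites 3 × 0.10 = +0.30; total -0.50 + 0.30 = -0.20. The signs are opposite.
- O = 3, r = 0.25: other sites +0.30; total -0.25 + 0.30 = +0.05.
- O = 5, r = 0.50: other sites +0.50; total -0.50 + 0.50 = 0.
- O = 20, r = 0.50: other sites +2.0; total -0.50 + 2.0 = +1.5.

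With no change elsewhere (g = 0), and with H from 0.25 to 3, O from 0 to 5 and r of 0.25 or 0.50, the total falls by 0.0625 to 1.5 units. That is 1.2% (0.0625/5.25) to 50% (O = 0, r = 0.50) of its baseline, although untreated sites have not moved.

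**Visits (a separate, clerical matter).** The total VASI visits also disagree:

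- Synopsis, Statistical Methods: Weeks 4 to 24 and 48, labelled Visits 5-15.
- Sections 6.4.3 and 6.4.4: Visits 7 and 10.
- Section 8.1.4: Visits 7, 10 and 14 after baseline.
- Section 11.2: Visits 7 and 14.
- Section 6.3, later table: Visit 14. The Visit 14 list (6.4.8) omits it, and the Visit 15 list (6.4.9) includes it.
- Section 6.3, first table, in the text available: Weeks 16 and 28. This may be a column shift from extraction, and nothing here rests on it.

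**The case against.** The strongest reply is that this is a wording slip in a measure of little weight. Total VASI is limited to description, in an unpowered, open-label, single-arm pilot whose primary endpoint is image analysis. Section 8.1.4 already words the purpose correctly, and copying that wording into the synopsis and Section 11.2 would remove the contradiction. This stands as a limit on the harm. It does not make the present statement true, and rewording alone would leave no summary aimed at untreated skin, which is what the plan says it wants.

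Second, the sizes are assumed. At the only documented anchor, the 0.25% entry minimum, a 50% fall hides 0.125 units. For one hand unit, a single step on the depigmentation scale from 10% to 25% is 0.15 units and from 25% to 50% is 0.25. This also stands: the masking may be small, and its size is unknown.

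Third, F-VASI uses the same method, is scored at Visits 7, 10 and 14, and must take in new facial patches, so a reader has real context for the face. That is fair for the face within the mask, but not for the neck or the treated areas outside the mask.

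Fourth, a five-site score is not a pure measure of untreated skin. It drops untreated head/neck skin, is 0 at baseline for subjects without lesions elsewhere, and can be affected by other therapy. All of this is true and should be stated with the table. It still excludes the treated face and neck, which the six-site total does not.

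**Conclusion.** The concern holds. Followed exactly, the plan produces a table that does not measure its stated target, because the treated head/neck is one of the six summed sites and no planned output removes it. This rests on the documents' own definitions and needs no numerical assumption.

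The size is unknown. In the assumed cases the error ranges from a reversed sign (-0.20 against +0.30) to a modest understatement (+1.5 against +2.0), and it is negligible when non-facial disease is extensive. No test, primary endpoint or decision depends on the measure. It is a correction that should be made, with modest consequences if it is not.

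**What to change.** 1. In Sections 8.1.4 and 11.2, add a descriptive VASI excluding head/neck: the sum of the other five sites. Summarise its change from Visit 2 at each post-baseline total VASI visit, and give the number of subjects scoring 0 at baseline.
2. Keep the six-site total, but describe it in Sections 1 and 11.2 as whole-body status, in line with Section 8.1.4.
3. State the limits of the five-site score. It leaves out untreated head/neck skin (eyelids, mucosal lip, and scalp, which is not listed as treated) and is not a control for facial change. It should be read beside the concomitant therapy log, because Section 5.6 permits NB-UVB after Visit 9 without naming a body area and permits topical corticosteroids away from the face and treated neck. Item 3 of Section 5.6.1 bars topical treatments that may affect vitiligo, so those two passages need reconciling.
4. If site-level values are not held and cannot be entered from source, correct the purpose wording only.
5. Reconcile the total VASI visits across the synopsis and Sections 6.3, 6.4.3, 6.4.4, 6.4.8, 6.4.9, 8.1.4 and 11.2, so that the Visit 14 reading needed by Section 11.2 is on the Visit 14 list. Check the 6.3 columns against the original table first.

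The cost is one descriptive table with one count, plus wording and visit-list edits. No new procedure or visit is needed, since each site is already evaluated. The documents do not show whether the eCRF holds site values, so some entry from source may be required.

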During the screening period, subjects will be assessed for eligibility to receive study medication. Eligible subjects will apply study medication to the vitiliginous areas of the face and neck and a ½" margin around these areas (excluding upper and lower eyelids [defined as the area from the bony rim of the orbit to and including the eyelids], and mucosal lip area) twice-a-day for up to 48 weeks. If applicable, the subject may treat up to the vermillion border of the mucosal lip and the skin underneath the beard. Assessment of response to treatment will be performed using Canfield 2-D photographic digital image analysis, Facial VASI, Vitiligo Noticeability Scale (VNS), VitiQoL and Subject Vitiligo Satisfaction Scale. These will occur as specified in the Schedule of Assessments. Subjects will be seen at up to 15 study visits, including up to 48 weeks of active treatment followed by a 4-week post-treatment follow-up visit. Subjects who consented for the original study treatment period for up to 28 weeks, and do not consent for the additional visits (Visit 12-15) will complete the study at Visit 11 (Week 28.) Safety and tolerability will be evaluated throughout the study by assessment of electro-cardiograms (ECG), clinical laboratory tests, adverse events including local site reactions, and vital signs.	
Number of Subjects (planned): Approximately 33 subjects will be enrolled.	
Number of Study Sites: This study will be conducted at approximately 5 U.S. clinical sites.	

Inclusion Criteria:

In order to be eligible for the study, a subject must fulfill all of the following criteria:

1. Subject is a male or female \geq 18 years of age.
2. Subject has a clinical diagnosis of new onset or actively progressing non-segmental facial vitiligo or worsening of existing facial lesions within the past 6 months. Actively progressing vitiligo is defined as: subject history of a new vitiliginous lesion or objective signs of disease activity (such as: confetti-like depigmentation, trichrome lesions, and the Koebner phenomenon) as assessed by the investigator. Subjects may have non-facial vitiliginous lesions that are unchanged for more than 6 months provided they meet the requirement for active facial lesions.

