6. INVESTIGATIONAL PLAN

6.1. Overall Study Design

This Phase 2, multicenter, open label study is designed to evaluate the safety, tolerability and efficacy of ATI-50002 Topical Solution in subjects with facial non-segmental vitiligo. Subjects will be required to have a clinical diagnosis of new onset or actively progressing non-segmental facial vitiligo involving at least 0.25% TBSA (excluding upper and lower eyelids, mucosal lip areas, beard [if applicable]; and forehead and chin areas covered by the stereotactic positioning device for photography) with at least one area of the face with normal pigmentation. The face is defined as the area from the border of the hairline, not including hair bearing skin to the jawline. Thirty-three subjects will receive ATI-50002 Topical Solution, 0.46%, BID for up to 48 weeks.

During the screening period, subjects will be assessed for eligibility to receive study medication. Eligible subjects will apply study medication to the vitiliginous areas of the face and neck including $\frac{1}{2}$ " margin around these areas (excluding the upper and lower eyelids and mucosal areas of the lips) twice-a-day for up to 48 weeks. Assessment of response to treatment will be performed using the Canfield 2-D Photographic image analysis, Facial VASI, Vitiligo Noticeability Scale, VitiQoL, and Subject Vitiligo Satisfaction Scale. These assessments will occur as specified in the Schedule of Assessments. Subjects will be seen at up to 15 study visits, including up to 48 weeks of active treatment followed by 4 weeks of post treatment follow-up.

Safety and tolerability will be evaluated throughout the study by assessment of electrocardiograms (ECG), clinical laboratory tests, adverse events including local site reactions and vital signs.

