9.1.4. Adverse event reporting period

The investigator must start reporting non-serious AEs with the subject's first study medication application and continue reporting until the end of the subject's last study visit. Reporting for SAEs must start when the subject signs the ICF and continue until the end of the subject's last visit.

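### The pooled TEAE proportion mixes about 28 and about 52 weeks of observation, so if first events occur late it is not a risk over any fixed window

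*Combined protocol and SAP*

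**What the plan says.** Section 11.2 gives one kind of adverse event summary. It states: "The proportion of subjects with treatment-emergent adverse events will be tabulated and presented by Medical Dictionary for Regulatory Activities (MedDRA) System Organ Class". It then adds: "Adverse event summaries will be presented showing the proportion of subjects experiencing adverse events, both overall and by MedDRA System Organ Class". These cover all enrolled and treated subjects. AE listings are also planned. The by-visit descriptive statistics (N, mean, median, SD) do not supply an AE incidence by period.

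Planned follow-up has two lengths. The Synopsis says that subjects from the original treatment period who "do not consent for the additional visits (Visit 12-15) will complete the study at Visit 11 (Week 28") leave at that point. The others have up to 15 visits, "including up to 48 weeks of active treatment followed by a 4-week post-treatment follow-up visit", so their last visit is at Week 52. Under Sections 6.4.4 and 6.4.5, continuation requires a new consent at Visit 10 or Visit 11.

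Section 9.1.4 starts non-serious AE reporting at the first application and has investigators "continue reporting until the end of the subject's last study visit". TEAE appears in the list of abbreviations, but its time window is not defined there, in Section 9 or in Section 11.2.

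**The concern.** Subjects with an event divided by subjects treated is a risk only when everyone is observed for about the same time. Here some subjects are observed nearly twice as long as others (52/28 = 1.86). Who falls in which group depends on re-consent and, by a footnote to the Schedule of Assessments, partly on when the amendment reached the site.

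Safety and tolerability belong to the primary objective (Section 4.1). The extension is also where other safety information is thinner: Section 8.2.5 schedules the Local Tolerability Assessment only for Visits 2 to 11, and it is absent from the Visit 12 to 15 schedule. AE reports therefore carry most of the local tolerability information for that period, and the pooled proportion does not isolate it. NB-UVB is allowed after Visit 9 (Section 5.6), so late risk may differ from early risk, and one cumulative proportion cannot show that.

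**Working it through.** **Inputs from the documents.** N: "Thirty-three subjects will be enrolled" (Section 11.1). Observation windows: about 28 and about 52 weeks (Synopsis, Section 9.1.4). Section 11.1 also says "A formal power calculation was not performed". The plan states no TEAE rate and no continuation rate, so it has no figure of its own to reproduce.

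**Assumptions (not in the documents).** Risk of a first TEAE by Week 28, R28, of 20%, 40% or 60%; constant hazard; no early withdrawal; c of 33 subjects continue.

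**Formulas.**

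- h = −ln(1 − R28)/28
- R52 = 1 − exp(−52h)
- Pooled proportion = [(33 − c) × R28 + c × R52]/33

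**Worked case, R28 = 40%.** h = 0.5108/28 = 0.01824 per week. R52 = 1 − exp(−0.9487) = 61.3%. With 17 continuing: (16 × 0.400 + 17 × 0.613)/33 = 51.0%.

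| R28 | R52 | c = 0 | c = 8 | c = 17 | c = 25 | c = 33 |
|---|---|---|---|---|---|---|
| 20% | 33.9% | 20.0% | 23.4% | 27.2% | 30.6% | 33.9% |
| 40% | 61.3% | 40.0% | 45.2% | 51.0% | 56.1% | 61.3% |
| 60% | 81.8% | 60.0% | 65.3% | 71.2% | 76.5% | 81.8% |

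In the middle row the expected number of subjects with an event goes from 13.2 to 20.2, although the hazard is the same throughout.

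**Sensitivity to late events.** Let the hazard after Week 28 be k times the early one, so R52 = 1 − exp(−28h − 24kh). With R28 = 40% and 17 continuing, the pooled figure is 51.0% for k = 1, 46.1% for k = 0.5, 43.2% for k = 0.25 and 40.0% for k = 0. The shift disappears when no first TEAE occurs after Week 28.

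**Sensitivity to the TEAE window.** If only on-treatment time counted (24 or 48 weeks), the same hazard gives 35.5% with none continuing, 47.2% with 17 and 58.3% with all. The pattern is the same.

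**What does not move.** In the middle row the Week 24 risk is 1 − exp(−24h) = 35.5% whatever c is. The rate to first event is 95.2 per 100 person-years whatever c is, but only because the hazard was assumed constant.

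**The case against.** **The Visit 10 analysis.** Section 11.1 plans initial analyses once all subjects complete Week 24, and a safety summary at that point could approximate a Week 24 incidence. This is a fair point, but no AE cut-off is stated. With the 12-week enrolment period in the Synopsis, the earliest enrollees could be near Week 36 (24 + 12) when the last subject reaches Week 24. Nothing says that a Week 24 figure is carried into the final report.

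**Size of the study.** This is a single-arm, descriptive pilot of 33 subjects. No decision rule uses the figure, and its sampling error is wide: an exact 95% interval for 9 of 33 runs from 13% to 46%. That stands and lowers the severity. It does not tell the reader which period the figure describes.

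**Listings.** The planned AE listings may let a reader reconstruct timing, but they are not a planned summary by period.

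**Stronger readings the documents do not support.** A reader might infer that the pooled figure always overstates 24-week risk and understates 48-week risk. But 24 and 48 weeks are treatment durations; AE collection runs to about Week 28 or Week 52. Take a constant hazard with 20% risk by Week 24, hence 36% by Week 48. Then R28 = 1 − 0.8^(28/24) = 22.9% and R52 = 1 − 0.8^(52/24) = 38.3%. The pooled figure is 27.5% with 30% continuing and 36.8% with 90% continuing, and the latter exceeds the 48-week risk. If no first events occur late, there is nothing to understate. A reader might also conclude that the figure cannot be compared with any other study. That goes too far: a crude incidence shown with its exposure is still usable.

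**Conclusion.** The point holds for the final pooled TEAE table. Section 11.2 states one crude proportion over two planned observation lengths, with no cut-off and no period summary. If first TEAEs occur after Week 28, the result depends on how many subjects continue.

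Under the illustrative 40% setting, the range between none and all continuing is 21.3 percentage points (61.3 − 40.0); under the 20% setting it is 13.9 points (33.9 − 20.0). Both rest on assumed rates, a constant hazard and no early withdrawal. The shift is smaller if the late hazard falls and nil if no first event is late.

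Severity is minor to moderate. The harm is to the interpretation of a primary-objective summary; no test or between-arm contrast is involved.

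**What to change.** In Section 11.2, define the TEAE window and specify:

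1. TEAE incidence from first application to a per-subject cut at Week 24 (Visit 10), in all treated subjects. Use the same cut at the initial and final analyses, and show how many withdrew before it.
2. TEAEs with onset after that cut in subjects who continued or re-started study medication, with that group as the denominator. Show post-treatment follow-up events separately, and state where events are counted that fall in an off-drug gap before a re-start at Visit 11. Label the table as conditional on continuing.

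Keep the overall crude column, labelled with median exposure. Give patient-year rates only as supportive: they assume a roughly constant hazard, which NB-UVB after Visit 9 makes doubtful, and stopping unrelated to tolerability.

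The cost is wording, a few table columns and small denominators in the extension table. No visit, treatment or sample size changes. AE records (Section 9.2.1) and dispensing dates (Sections 7.2 and 7.7) are already collected; the AE eCRF must carry onset dates.
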